#### a. Interventions and Observations:

If CECS is diagnosed by intramuscular pressure (IMP) elevation, patients will be offered Botulinum toxin injection regimen into the affected compartment or referral to orthopedic surgeon for a possible surgical fasciotomy. Patients will be provided information regarding both Botulinum toxin injections and fasciotomy. Patients will be allowed to discuss fasciotomy with a surgeon prior to making a decision to participate in the study, if desired. Potential side effects of Botulinum toxin injection include possible bleeding, pain, infection, general muscle weakness, muscular atrophy, flu-like symptoms, breathing and swallowing difficulties and death. Potential side effects of fasciotomy include surgical site pain, bleeding, recurrence of symptoms, scarring, muscle weakness, nerve damage, hematoma, need for repeat operation, infection, reactions to anesthesia (e.g. anaphylaxis), blood clot, muscle wasting (atrophy), and death. These will be explained to participants during the consent discussion.

For those diagnosed with CECS and desire Botulinum toxin injections, they will receive 2 injections per affected compartment. Up to 50 units of Botulinum toxin will be injected into the proximal and distal portions of the compartment for a maximum total dose of 100 units. A solution of 100 units of Botulinum toxin per 2 mL of normal saline will be used for all injections. Standard sterile technique will be followed. Insertion in to the correct compartment will be accomplished using general landmarks. The compartment will be separated into thirds measuring from the tibial plateau to the head of the calcaneus. Injections will be given at approximately 1/3 the distance from the tibial plateau for the proximal injection and 2/3 the distance from the tibial plateau for the distal injection. If the lateral or deep posterior compartment is affected, a total of 50 units Botulinum toxin will be given, 25 units per injection. If the anterior or superficial posterior compartment is affected, a total of 100 units Botulinum toxin will be given, 50 units per injection. Of note, CECS mainly affects the anterior and lateral compartments and is rarely seen in the superficial posterior or deep posterior areas.

For those diagnosed with CECS and desire surgical fasciotomy, the team will discuss the fasciotomy procedure and risks as mentioned above. For the procedure, the patient will be placed under general anesthesia and then linear incisions will be made into the affected compartment releasing the underlying fascial layer, reducing the pressure of the compartment. The entire procedure will be accomplished in a sterile fashion. Further details and scheduling will be per the orthopedic surgeon's recommendations.

After the initial Botulinum toxin injection regimen or fasciotomy, patients will be assessed at 1 month, 3 months, and 6 months with the LEFI and universal pain scale. Primary outcome will be pain reduction. Adequate pain reduction will be rated as less than 3 on the universal pain scale. Secondary outcomes will include return to full activity and patient satisfaction. Full activity is defined as able to run 1.5 miles and complete work duties with either no pain or pain that can be ignored. To assess patient satisfaction, patients will be asked if they were or were not satisfied with the Botulinum toxin injections at the 6 month visit.

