#### d. Subjects:

Patients will be active duty military adults, 18 years of age or older, who have clinical signs and symptoms of chronic exertional compartment syndrome in any muscular compartment of the lower leg. All patients referred to the sports medicine clinic for leg pain will be screened for possible inclusion into the study, following standard of care clinical tests. After an initial standard of care evaluation, if CECS is suspected, each subject will be asked to participate in the study and will be formally consented by a member of the research team.

Other exertional causes of leg pain will be ruled out by a standard of care clinical examination (general, orthopedic, neurologic, and functional) and supporting workup. This will include plain radiographs of the knee, tibia, fibula, and ankle on the affected side of the lower extremity. Any patient with an abnormal finding not consistent with CECS, such as a stress fracture, will be ruled out from participating in the research study. Patients will have tried conservative treatment for at least 2 months prior to compartment testing to include rest, stretching, ice, and NSAIDs. All patients reporting lower extremity pain will be examined by a physician on the study team to confirm CECS under the direct supervision of [name].

Intramuscular pressure in lower leg compartments will be obtained by IMP needle insertion (standard of care) into all four compartments of both lower legs before and after exercise. Infection risk will be decreased by sterilizing the puncture site with chlorhexidine swabs. Pain will be decreased by injecting 0.5 mL of 1% lidocaine with epinephrine superficially to anesthetize the skin. Pressure will be transmitted to a pressure transducer for measurement in mm Hg. The exercise portion will be standardized by having patients run on the same treadmill with enough speed until their symptoms begin. After symptoms begin, the patient will be asked to continue running until he or she cannot tolerate, at which time the exercise will be stopped and the patient will lie supine for repeat intramuscular pressure measurements. Definitive diagnosis of CECS will be based on intramuscular pressure elevations according to Pedowitz et al. This includes 1) a pre-exercise pressure greater than or equal to 15 mm Hg and 2) a 1-5 minute post-exercise pressure of greater than or equal to 30 mm HG.

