# 10. DRUGS, BIOLOGICS, DIETARY SUPPLEMENTS, AND MEDICAL DEVICES

Does the study plan dictate the use of any of the following?		
A drug	✓ Yes	□ No
A biologic	Yes	☑ No
A compound intended to affect structure or any function of the body	Yes	☑ No
A dietary supplement or substance generally recognized as safe that will be used to diagnose, cure, mitigate, treat, or prevent disease	Yes	☑ No
A medical device	Yes	☑ No

10A. List all drugs covered by an Investigational New Drug (IND) from the FDA (approved or submitted)						
Name of Drug Dose(s) direct		ted by	Route(s) of	IND Number or		IND Holder
riams of Drug	protocol		administration	Date S	Submitted	(Sponsor)
Botulinum Toxin	50-100u		IM	134278/Exempted		
10B. List all FDA appr	oved drugs bei	ng usec	l in accordance with FI	ОА аррі	oved labeling	
Name of Drug		Dose(	s) directed by protocol	Route(s) of ad		dministration
☑ N/A, no FDA appro	ved drugs being	used a	ccording to the labeling			
10C. List all FDA approved drugs used for an unapproved use ("off-label")						
Name of Drug Dose(s) directed by protoco			Route(s) of administration			
Botulinum Toxin	50u per injection		IM to treat CE	IM to treat CECS		
10D. List all biologics, compounds and dietary supplements						
✓ N/A, no biologics, compounds and dietary supplements						
10E. List all devices covered by an Investigational Device Exemption (IDE) from the FDA (approved or submitted)						
✓ N/A, an IDE has not been submitted to or approved by the FDA						
10F. List all FDA approved devices used for an unapproved use ("off-label")						
☑ N/A, no FDA approved devices being used "off-label"						
10G. List all unapproved devices.						

59th Medical Wing Institutional Review Board

✓ N/A, no unapproved devices					
10H. Device Storage					
Location(s):					
Is this research an "applicable clinical trial" which must be registered on ClinicalTrials.gov?					
x Yes, Local Investigator registered the trial NCT03339921					
Use of a placebo in place of standard therapy:					
Is a placebo being used in place of stand	ard 🗹 No	□ Yes			
therapy?	 	 			

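### The 100-unit maximum and the 50-100u entry in section 10A do not say whether they apply per compartment, per leg or per patient, although eligibility does not limit the number of compartments or legs

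*Combined protocol and SAP*

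**What the plan says.** The relevant statements are in three places of the combined protocol and SAP.

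- **Section 3a, Interventions and Observations.** Patients who choose toxin are told that "they will receive 2 injections per affected compartment". The next sentence reads "Up to 50 units of Botulinum toxin will be injected into the proximal and distal portions of the compartment" and ends "for a maximum total dose of 100 units". Totals by compartment type follow. For lateral or deep posterior disease, "a total of 50 units Botulinum toxin will be given, 25 units per injection". For anterior or superficial posterior disease, "a total of 100 units Botulinum toxin will be given, 50 units per injection". The paragraph closes by noting that "CECS mainly affects the anterior and lateral compartments".
- **Section 3d, Subjects, and the Inclusion/Exclusion Criteria.** Disease in any lower-leg compartment qualifies. Intramuscular pressure (IMP) is measured "into all four compartments of both lower legs before and after exercise". The exclusions that concern the limb are prior toxin and prior release. Nothing limits the number of qualifying compartments or excludes two-leg disease.
- **Section 10.** Item 10A, the entry for the drug under the IND, gives 50-100u with no reference unit. Item 10C gives "50u per injection".

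No section says how the dose is set or limited when several compartments meet the pressure criteria.

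**The concern.** Testing all four compartments in both legs will detect multi-compartment and two-leg disease where it exists, so the question of a patient's total dose can be expected to arise. Two physicians following the same text could then act differently. One takes 100 units as the patient's limit and departs from the instruction to inject each affected compartment at its stated total. The other takes it as a compartment limit, injects every qualifying compartment, and gives a patient total outside the 10A range.

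Two things are at stake.

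- **Exposure.** The plan lists general weakness, breathing and swallowing difficulties and death among the toxin risks, and marks data safety monitoring as not applicable. The permitted exposure of a patient should not depend on how a sentence is read.
- **Interpretation.** The primary outcome is pain below 3, and full activity requires a 1.5-mile run. A qualifying compartment left uninjected could produce a failure on either outcome that says nothing about efficacy. The list of clinical data for analysis in section 3 includes neither the compartments injected nor the total dose, so such failures could not be identified. The Background also states an interest in dose-dependent effects, which requires a defined and recorded dose.

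**Working it through.** **Inputs, all from section 3a and section 3d**

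- Injections for each affected compartment: 2.
- Units per injection: 25 (lateral, deep posterior) or 50 (anterior, superficial posterior).
- Compartments tested: 4 in each leg × 2 legs = 8, of which four carry the lower total and four the higher.
- Stated maximum: 100 units. Section 10A: 50-100u.

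**Step 1. Reproduce the stated figures.** Total for one compartment = injections × units per injection.

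- Lateral or deep posterior: 2 × 25 = 50.
- Anterior or superficial posterior: 2 × 50 = 100.

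The maximum of 100 and the range of 50 to 100 are exactly the figures for one compartment.

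**Step 2. Sum over compartments.** Patient total = sum of the compartment totals.

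| Affected compartments | Sum (units) | Within 100 if per patient? |
|---|---|---|
| Both lateral | 50 + 50 = 100 | Yes |
| Lateral + deep posterior, one leg | 50 + 50 = 100 | Yes |
| Anterior + lateral, one leg | 100 + 50 = 150 | No |
| Both anterior | 100 + 100 = 200 | No |
| Anterior + lateral, both legs | 2 × 150 = 300 | No |
| All eight | 2 × (100 + 100 + 50 + 50) = 600 | No |

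**Step 3. Count every possible pattern under a per-patient reading.** There are 2^8 − 1 = 255 non-empty sets of the eight compartments.

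- One compartment: 8 of 8 fit.
- Two compartments: 28 pairs. Six are pairs of 50-unit compartments (sum 100, fit), 4 × 4 = 16 are mixed (sum 150) and six are pairs of 100-unit compartments (sum 200). So 6 of 28 fit.
- Three or more: 255 − 8 − 28 = 219 sets. The smallest possible sum is 3 × 50 = 150, so none fits.

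In all, 8 + 6 = 14 of 255 patterns fit. This counts combinations. It does not estimate patients, because the patterns are not equally likely and the plan gives no frequencies.

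**Step 4. Per-leg reading.** Within one leg, the four single compartments and the lateral plus deep posterior pair fit; anterior plus lateral (150) does not. Both anterior compartments would now fit, at 100 in each leg. This reading removes some of the conflicts and leaves others.

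**Step 5. Per-compartment reading.** Every pattern agrees with section 3a. The patient total then ranges from 50 (one lateral or deep posterior compartment) to 600 (all eight), with no limit stated at patient level. The 10A range is then correct only as a range for one compartment, which 10A does not say.

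**The case against.** The strongest reply is that the maximum is evidently per compartment. The sentence that carries it refers to a single compartment, follows directly on an instruction given for each compartment, and 2 × 50 = 100 is the largest compartment total. The two later totals in the paragraph are also compartment totals. This reading is plausible, and it stands as far as section 3a is concerned: the section is then consistent for every patient. It does not settle the patient's total dose, which is then unlimited in the text, or 10A, which then describes one compartment without saying so.

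A reader might infer more than the documents support:

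- **That the stated figures fit only one-compartment disease.** They do not fit only that. Any two lateral and/or deep posterior compartments sum to exactly 100.
- **That multi-compartment patients cannot be treated in line with the text.** This presupposes a per-patient maximum, which section 3a does not state.
- **That treatment would breach the IND terms.** The plan records the IND as exempted and lists the investigational-drug form and the FDA determination letter as attachments. They are not available here and may define the dose basis.
- **That a particular number of patients is affected.** The share with multi-compartment or two-leg disease is not given. The 15 prospective patients may include fasciotomy patients, since section 3 describes both arms prospectively, although section 3c describes the prospective portion in terms of toxin recipients only.

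It is also fair to say that 10A is a short form entry and that 10C is expressed per injection, so section 10 is not clearly a statement of cumulative patient dose. The 600-unit total is a bound: the plan itself calls superficial and deep posterior disease rare. Anterior plus lateral disease is different, because those are the two sites that the plan names as the main ones.

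**Conclusion.** The reference unit of the 100-unit maximum and of the 10A range is undefined, and this needs correction under any reading. Read per patient, both figures conflict with the plan's compartment totals for most multi-compartment patterns: 22 of 28 pairs and all 219 larger sets, including anterior plus lateral in one leg at 150 units. Read per compartment, section 3a holds together, but 10A does not describe a multi-compartment patient's dose, and the patient total is left open between 50 and 600 units.

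The arithmetic rests only on the plan's own compartment totals and on the absence of any limit on compartments or legs in the eligibility text. It assumes nothing about how common multi-compartment disease is, so the number of trial patients affected is unknown. The text does not determine a multi-compartment patient's exposure to the investigational drug, which bears on both safety and the reading of treatment failures. That makes it more than a missing detail.

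**What to change.** The sponsor should reconcile section 3a, section 3d, the Inclusion/Exclusion Criteria and section 10:

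1. State whether the maximum applies per compartment, per leg or per patient.
2. Express the 10A entry in the same unit. While section 10 is open, reconcile 10C, which lists only 50 units per injection, with the 25-unit injections in section 3a.
3. Make the eligibility criteria (number of compartments, one or both legs) consistent with that statement.
4. For each injected patient, record which IMP-positive compartments were treated, which were not, and the total dose given, so that failures with untreated disease can be identified.

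Which limit applies is for the sponsor to settle with the IND documents; none is proposed here.

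The cost is a wording amendment and a small addition to data collection. Depending on the sponsor's answer, the eligibility of some multi-compartment patients may change, which would matter in a study that already expects few patients.

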# 2. RESEARCH PLAN

#### **Purpose of Study:**

Chronic exertional compartment syndrome (CECS) is a debilitating condition that causes elevation in compartment pressure, which can restrict patients from work and exercise. Typical treatment is to relieve compartment pressure though surgery. While surgery is effective for 66% of patients, it comes with increased risk and typically takes at least 8-13 weeks for full return to activity. One unproven alternative for pain relief is the use of botulinum toxin, a paralyzing agent. Botulinum toxin injections into the affected area in the lower extremities have been shown in limited trials to be a potentially cost effective way to relieve pain and return patients to full activity faster. Therefore, we will investigate the feasibility of a simple outpatient one time injection regimen for the treatment of CECS. We think botulinum toxin injections will be a potentially cost-effective, low-risk alternative to surgery in reducing pain and returning patients to full activity.

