## **Background and Review of Literature:**

The long term objective of this project is to validate botulinum toxin injections as a non-inferior treatment option for pain control and ability to return to full activity for adult military members suffering from lower extremity Chronic Exertional Compartment Syndrome (CECS), when compared to surgical fasciotomy. CECS is a debilitating disorder in which pressure in muscle compartments increases with exercise and resolves with rest. This causes pain, paresthesia, and inability to tolerate exercise. CECS mainly afflicts the lower extremities, below the knee, but upper extremity CECS has also been reported. CECS mainly affects young active adults. At risk groups include males, active duty military members, and athletes, both professional and recreational. 1,3,4,5

The current standard for definitive management and treatment of CECS is surgical fasciotomy. According to a 2016 systematic review, surgical intervention for CECS is successful in only 66% of those affected, with 13% of patients reporting complications from surgery, and 6% needing a repeat procedure. Definition of success varied across studies, but included patient satisfaction, lack of surgical revision, and full return to activity. Besides risks and complications, surgery also required a mean of 13 weeks to return to full activity when effective. A 2011 Cohort showed 81% overall patient satisfaction with the procedure, but noted best results from fasciotomy were young participants <23 years old, who underwent isolated anterior compartment release. Satisfaction was defined as being pain free or significantly improved on a 5 point pain scale, varying from pain free to worse. A smaller 2014 retrospective chart review of elite athletes with CECS showed fasciotomy was initially successful in 85% with a mean return to elite activity of 10.4 weeks. However, 30.8 % had a return of symptoms within the follow-up period.

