### 3. RESEARCH DESIGN AND METHODS

## **Research Design and Methods:**

The study will be a prospective cohort pilot study designed to compare Active Duty patients, 18 years of age or older, with CECS undergoing two different treatment interventions. The first arm will be patients receiving investigational botulinum toxin injections. The second arm will be patients who undergo the standard of care surgical fasciotomy. Both arms will be evaluated for pain relief with the universal pain scale and lower extremity functional index (LEFI) surveys at pre-treatment and again at one, three, and six months post-treatment. At the six month follow up, subjects will be asked the Satisfaction Survey (in-person, via Survey Monkey or Google Forms). Clinical data that will be analyzed for research purposes in both groups include age, sex, height, weight, body mass index, time to diagnosis, minutes of exercise prior to onset of symptoms, minutes of rest before relief of symptoms, LEFI and pain on the Universal Pain Assessment Tool.

In addition, we will be conducting a retrospective review from July 1, 2016 through June 30, 2017 of patients who have been diagnosed with CECS and have undergone surgical fasciotomy. They will be asked to recall their symptoms both before and six months after their surgery, in order to complete the LEFI and Universal Pain Assessment Tool (in-person, via Survey Monkey or Google Forms). They will also be asked if they were satisfied with their treatment. A HIPAA Waiver Request will be used to access medical records and contact these individuals, followed by each subject being verbally consented to participate in the study prior to completing the LEFI and universal pain scale surveys (in-person, via Survey Monkey or Google Forms). If the subjects refuse to be consented, then no data will be gathered from the subjects or their medical records.

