# **Inclusion/Exclusion Criteria:** · Adult ages 18-65 · Active duty military Unable to run 1.5 miles without producing symptoms, including aching, burning, numbness, tingling, or weakness in the affected limb Failed conservative treatment over a period of 2 months, including trial of rest, Inclusion Criteria NSAIDs, icing, and stretching routine Meets standard of care clinical diagnostic intramuscular compartment pressure criteria for CECS, based on standardized IMP needle testing. See below for testing protocol and criteria. · Prior Botulinum toxin injections into the affected limb Prior compartment release of the affected limb **Exclusion Criteria** Pregnant or becomes pregnant during the study Standard of care clinical exams indicating other more likely causes of leg pain

t. Source	r. Source of Research Material:							
Will you be using private information in this study?				□ No – Only using publically available information □ Yes –				
-	☑ protected	health informati	on (PHI)		y a covered entity			
	other type:	s of private info	rmation	Desc	cribe:			
If Yes,	research information (non-PHI) that is not publically available (i.e.,			Describe:				
	student record	ds)						
Use of iden information	itifiers with pri 1	vate						
Identifiers t	to be Used?	Column A Looked at by research team	Colum Record on enrollm log, sub list, or	ded nent oject key	Column C Recorded on data collection tool (survey, spreadsheet, etc.)	Column D Recorded on specimen containers	Column E Shared w/ others not on research team	Stored after study ended

NONE						
Names	V	V	V			
Study codes linked to individuals' identities using a key only accessible by the					_	
researcher						
Addresses						
Dates (except year)	~	✓	>			
Ages over 89						
Phone/Fax Numbers	>	~	<			
E-mails						
- SSNs	V	~	~			
- Scrambled SSNs	Specify:	Specify:	Specify:	Specify:	Specify:	Specify:
- last four of SSN	Last 4 SSN	Last 4 SSN	Last 4 SSN			
Numbers: - Medical record # - Account # - Certificate/license # - Health plan beneficiary # - Vehicle identifier/serial # - License plate #	Specify: Medical record #	Specify: Medical record #	Specify: Medical Record #	Specify:	Specify:	Specify:
- Device identifier/serial #						
Web URLs or IP addresses						
- Biometric Identifiers,						
including finger/voice prints - Full-face photo images and comparable images	Specify:	Specify:	Specify:	Specify:	Specify:	Specify:

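### The primary success rule (pain below 3) requires neither a score taken on exertion nor a pre-treatment score of 3 or more, so a patient whose CECS has not improved can be counted as a success

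*Combined protocol and SAP*

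**What the plan says.** Section 3a (Interventions and Observations) names pain reduction as the primary outcome and gives one criterion for it: "Adequate pain reduction will be rated as less than 3 on the universal pain scale". Outcome Measures in section 6 repeats the criterion and adds nothing to it. On timing, section 3a states that "patients will be assessed at 1 month, 3 months, and 6 months with the LEFI and universal pain scale"; Research Design and Methods adds a pre-treatment score. The plan's text gives no activity condition, recall period, required baseline level or required change, and does not say which of the three visits decides success.

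The Background describes the disease as follows: "CECS is a debilitating disorder in which pressure in muscle compartments increases with exercise and resolves with rest". The entry criterion on symptoms is "Unable to run 1.5 miles without producing symptoms, including aching, burning, numbness, tingling, or weakness in the affected limb". It ties entry to a run but sets no minimum pain score.

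Exertion enters the outcomes in two other places. One is a secondary outcome: "Full activity is defined as able to run 1.5 miles and complete work duties with either no pain or pain that can be ignored". The other is a pair of items in the list of clinical data to be analysed, "minutes of exercise prior to onset of symptoms, minutes of rest before relief of symptoms", with no visit stated. Statistical Analysis in section 6 describes the primary measure as a comparison of pain before and after treatment within each regimen. Data Analysis in the same section plans a comparison between the two treatments and bases its power figures on the proportion scoring below 3.

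**The concern.** A low score shows treatment benefit only if the patient was doing what normally provokes the pain, and had pain at that effort beforehand. The responder rule asks for neither. For a condition that settles with rest, a score given by someone who is resting, or who has stopped running, may be low whether or not the treatment worked. A patient who qualified on tingling or weakness may have scored below 3 before treatment.

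Pain control is part of the non-inferiority hypothesis and of the second goal. Patients counted as successes whatever their response raise the rate in each arm. If their share is similar in both arms, the two rates move closer together, which favours a non-inferiority reading, and the plan states no margin. If the share differs, the comparison acquires a difference that is not due to treatment. A different share is plausible early on. The Purpose of Study says that surgery "typically takes at least 8-13 weeks for full return to activity", whereas the Background's single injection case report describes full recreational activity within 4 weeks.

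**Working it through.** **1. The passages side by side**

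| Element | What the plan's text fixes | What it leaves open |
|---|---|---|
| Success rule (3a; 6, Outcome Measures) | Score below 3 | Rest or exertion; recall period; baseline; deciding visit |
| Entry criteria | Symptoms on a 1.5-mile run; raised pressures | Any minimum pain score |
| Follow-up visits | LEFI and pain scale at 1, 3 and 6 months | Any provoking effort before or during scoring |
| Procedures table (section 3) | Four pain scores; one pressure test, none research-driven | Whether the four scores are taken under the same conditions |
| Retrospective group | Recalled scores, before and six months after surgery | Whether recall concerns rest or exertion |

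Three routes to a success without benefit follow: the patient is scored at rest; the patient avoids the provoking exercise; or the patient was below 3 before treatment.

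**2. What the pre/post comparison covers.** A patient who scores 2 before and 2 after meets the responder rule but contributes a change of 0 to the pre/post comparison. That analysis therefore limits the third route. It does not limit the first two if the earlier score reflects exertion and the later one rest, because the score then falls without any effect of treatment.

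**3. Timing.** Using 13 weeks per 3 months, the visits fall at about 4, 13 and 26 weeks. Against 8-13 weeks to full activity after surgery, a difference in activity between arms is plausible at 1 month, possible at 3 months, and should largely have passed by 6 months.

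**4. The plan's own figures.** For 67% versus p₂, two-sided alpha 0.05, 80% power and equal groups, with p̄ the mean of the two rates:

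n per group = [1.960·√(2p̄(1−p̄)) + 0.842·√(p₁(1−p₁) + p₂(1−p₂))]² / (p₂−p₁)²

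For p₂ = 85%: p̄ = 0.76; (1.960·√0.3648 + 0.842·√0.3486)² / 0.18² ≈ 87.2, so 88 per group and 176 in total. The five scenarios give 1008, 360, 176, 98 and 60, all as stated. The arithmetic is sound; the issue is what a score below 3 means.

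**5. Illustration only.** Let m be the share who score below 3 whatever the treatment does. The documents do not give m, so the values below are assumptions. Observed rate = m + (1−m)p, and the difference between arms is multiplied by (1−m).

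| m, both arms | Observed rates (true 67% vs 85%) | Difference | Power at N = 176 | N for 80% power |
|---|---|---|---|---|
| 0 | 67.0% vs 85.0% | 18.0 | 80% | 176 |
| 0.1 | 70.3% vs 86.5% | 16.2 | 75% | 202 |
| 0.2 | 73.6% vs 88.0% | 14.4 | 68% | 234 |
| 0.3 | 76.9% vs 89.5% | 12.6 | 61% | 276 |
| 0.5 | 83.5% vs 92.5% | 9.0 | 45% | 408 |

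If m = 0.3 in one arm only and the true rate is 67% in both, the observed rates are 0.3 + 0.7·0.67 = 76.9% and 67%, a spurious 9.9 points.

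**6. At the planned size.** With at most 15 prospective patients and 10 retrospective ones, one misclassified patient moves a group's rate by at least 1/15 = 6.7 points or 1/10 = 10 points.

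**The case against.** The strongest reply is that exertion and baseline are not ignored. The primary measure in Statistical Analysis is a pre/post comparison, in which a patient low throughout shows no gain. Return to full activity is tied to a 1.5-mile run and shares the second goal with pain control, and exercise minutes and the LEFI are also collected. This stands as mitigation. It does not repair the responder rule, which is the plan's only definition of adequate pain reduction and the basis of its power figures.

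The Universal Pain Scale is listed as an attachment and is not shown, so its wording may specify the kind of pain. That also stands: confidence should be moderate until the form is read. Patients are, moreover, screened because of leg pain, so entry on numbness alone is probably uncommon, though the criteria permit it.

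A reader might infer more than the documents support:

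- That untreated patients would be counted as successes. Both groups are treated; the point concerns unimproved patients and scores taken before treatment.
- That patients recovering from surgery will score below 3. The plan lists surgical site pain among the side effects of fasciotomy, so their scores could be higher.
- That the baseline score is taken at the treadmill run. The plan describes pressure measurement there and does not say when the pain score is given.
- That nearly everyone would score below 3 at rest. No such figure appears.

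**Conclusion.** The concern holds for the responder rule. As written, the rule can classify as a success a patient who is unimproved, inactive or low at baseline, because it asks for neither exertional pain nor a raised pre-treatment score. This is a fault in the rule and not merely missing detail, since following it exactly produces the misclassification. In the early visits the arms may also differ in activity.

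The size is unknown. The tabulated loss of power, from 80% to between 75% and 45%, rests on an assumed share of 10 to 50%, equal in both arms, and on the plan's hypothetical N of 176 rather than the 25 patients expected. The direction is firmer: an equal share draws the two rates together, and an unequal share creates a difference. The 67% planning rate offers no calibration, because the Background describes the 66% surgical success rate from a systematic review as resting on mixed definitions of success.

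The documents do not support saying that the primary analysis as a whole is invalid. The pre/post comparison keeps its value if scores are taken under the same conditions at every visit, which the plan's text does not require.

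**What to change.** Read the attached pain-scale form first. If it does not already fix the context of the score, make these changes in section 3a and in Outcome Measures:

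- Define the primary score as worst leg pain during running or equivalent exertion over a stated recall period. Ask it in the same words at pre-treatment and at 1, 3 and 6 months in both arms, and in the retrospective questionnaire.
- Count as a responder a patient with a pre-treatment exertional score of 3 or more and a follow-up score below 3. Report patients who start below 3 separately.
- At each visit record whether the patient was running or exerting. Report those who were not, with the reason, as their own category, neither as pain below 3 nor as automatic failures. Calling patients in surgical recovery failures would build recovery time into the pain endpoint, to the disadvantage of surgery, and would overlap with return to full activity.
- Use 6 months for the main comparison between treatments. It is the only post-treatment time shared with the retrospective group.

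The cost is one reworded question and one added item on forms already in use. The drawbacks are a smaller responder denominator in a prospective group of 15, and possibly lower success rates.
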